### ***Modifications to the Consent Process***

For the pilot, It should be noted that primary care sites are only obtaining authorization to share family contact information with the study team and not directly obtaining informed consent. Given the realities of community primary care (e.g., 15 to 20 minutes for an entire well child check), it is not possible for community primary care providers to obtain informed consent. In addition, doing so would require the study team to engage 30 community primary care providers in research, which it is unlikely that they would be consistently willing to do. Whenever possible, signed consent and authorization will be obtained electronically. However, we are requesting a waiver of consent documentation for families that cannot access the internet. This will allow us to obtain consent and authorization verbally for those individuals when it is not practicable to get signed consent and authorization. We have also submitted the necessary HIPAA documentation to allow for this verbal consent and authorization. Since families will be located all over the state of Oregon it will not be possible to mail and mail back a signed consent form in a timely way, and this delay might contaminate time-sensitive study outcomes. Therefore obtaining a signed consent in these cases is not possible.

For the expansion, we will need to obtain a HIPAA waiver to consent families off the Autism clinic waitlists. We are requesting a HIPAA waiver because it would not be possible to contact families to secure their interest in Autism ALERT without getting some information to contact them with. Having participating clinics contact families would place an unreasonable burden on clinic administrative staff, who are already overwhelmed by very long wait lists for autism services.

### ***Non-English Speaking Subjects***

Study materials will be available in English and Spanish. At the time of the referral, Spanish speaking patients can receive a study packet, including the study interest form, in Spanish. Navigator services in Spanish will also be available, so Spanish signed consent can be obtained by the study team. We cannot enroll non-English/non-Spanish speakers in the study, because

from a scientific standpoint their resource use would be quite different. In addition, the low numbers of enrollees in this group might create imbalances in the intervention and control arms that would make data interpretation challenging.

For the expansion, we will offer non-English/non-Spanish speakers the Autism ALERT navigation support; however, they will not receive the program evaluation measures because they have not been validated in other languages. We are working to make the evaluation measures available in more languages currently.

### ***Assent of Children and Parent Permission***

Since the children in the children/parent dyads in the study will be 5 years old or younger and have developmental difficulties, the capability of the children is so limited that they cannot reasonably be consulted about this research. For this reason, parental consent as described above and child assent will not be obtained.

### ***Adults Unable to Consent/Decisionally Impaired***

Adults who are unable to consent or who are otherwise decisionally impaired will not be considered eligible for the study at this time.

## **6) Procedures**

Data collected from children and families includes process data about interactions with families, family survey data, and administrative data about children's medical and educational services use. Process data about interactions with families will be collected by family navigators (who are part of the research team) using the Care Coordination Management Tool and the Navigator Fidelity Checklist, which are study tools adapted from existing measures. Only members of the study team will have access to these data, and these data will be securely kept on the OHSU Sharepoint secure cloud storage throughout the study. These data are collected for the purposes of evaluating this research project.

Survey data from families will be collected in both study arms primarily via a mailed and/or online survey. The survey will be sent upon enrollment and 6 months after enrollment in Autism ALERT or the comparison intervention. Prior to the 6 month post-enrollment survey, a letter will be sent to families informing them of the upcoming survey and the \$50 incentive for completion. A \$50 cash or gift card incentive will be provided for survey completion. The survey will initially be sent 3 times via a secure RedCap link. Then non-responders will be contacted via telephone. Subjects who do not respond to either email or telephone will be sent a survey mailing with a \$5 Dutch Bros coffee card. The survey will be marked with a study number only and will contain no personal identifiers. The study team will have a separate locked document that has the key linking study ID to personal information (see below). Completed surveys will be mailed back to the study team in an envelope and entered into a secure database behind the OHSU firewall. Original copies will be stored in a locked file cabinet in the study team area.

For the expansion, survey data from families will be collected primarily via a mailed and/or online survey. The survey will be sent upon enrollment and 6 months after enrollment in Autism ALERT. Prior to the 6 month post-enrollment survey, a letter will be sent to families

informing them of the upcoming survey and the \$10 incentive for completion. A \$10 cash or gift card incentive will be provided for survey completion. The survey will initially be sent 3 times via a secure RedCap link. Then non-responders will be contacted via telephone. Subjects who do not respond to either email or telephone will be sent a survey mailing with a \$5 Dutch Bros coffee card. The survey will be marked with a study number only and will contain no personal identifiers. The study team will have a separate locked document that has the key linking study ID to personal information (see below). Completed surveys will be mailed back to the study team in an envelope and entered into a secure database behind the OHSU firewall. Original copies will be stored in a locked file cabinet in the study team area.

Study team members will also be reaching out to families via email and/or phone, about participating in a semi-structured phone interview regarding their experiences with navigators, and the overall Autism diagnosis process. Families will be contacted via email and telephone to schedule these interviews. Participating families will receive \$50 for completing the interview. Interviews will be recorded using WebEx or a digital audio recorder. These recordings will then be sent to GMR Transcription (HIPAA-compliant) to provide transcripts. Finally, the study team will code the interviews using Dedoose software to get a better understanding of parents' experiences in the Autism evaluation process.

Administrative data about children from the ecWeb (EI/ECSE) database will be governed by a Data Use Agreement (DUA) between [name] (PI) and the Oregon Department of Education (ODE). Consistent with our prior DUA's, we will request ecWeb access for only families with signed consent and a FERPA release for each child's educational data. The study team will submit names and dates of birth of people who signed consent and authorization to ODE staff, and ODE staff will allow the study team direct access to these individuals' data within ecWeb, ODE's database for Early Intervention. ODE staff are only releasing data and will not be considered engaged in research. These data include details on the dates and times of each child's referral, evaluation, and service plan. ODE staff will provide access to these data, which study team members will analyze, and are not considered part of the study team.

After consent, secure emails may be transmitted between the family navigator and the PCP, which may contain family information. These emails will be sent via encrypted email using the OHSU Secure Mailbox. This technology requires outside users to log into a website behind the OHSU firewall to send/receive the encrypted email, which minimizes the risk of privacy breach. Secure messages also automatically expire 30 days after creation and are removed from the Secure Mailbox server. Autism ALERT will also have a PCP interface in which PCPs can contact the study team and monitor the status of their patients. This interface will be part of OHSU's RedCap database and thus will also be hosted behind OHSU's firewall. It will require a unique user ID and password, which the study team will assign to each PCP. Each PCP will only be allowed to view his/her own patients on the secure website.

We will also survey providers about intervention fidelity, feasibility and acceptability. Survey data on providers will be collected via a mixed mode (in-person, email, mail, fax) survey, upon enrollment, at the end of subject enrollment (about patient portal use only) and at the end of the study intervention period. The survey will be sent to all providers whose clinics participated in the study, whether or not they were assigned to the study intervention or actually used Autism ALERT. Surveys will initially be sent to providers in person or via an email link, which will connect to a secure RedCap server. The survey will require entry of a study number only and will contain no individual identifiers. Non-responders, identified by a locked

key document to associate their names with their study IDs, will be sent follow-up emails, and will also be given the option to complete the survey via mail or fax. Paper surveys will be stored securely at OHSU as outlined above and destroyed approximately 6 months after publication of study results. The patient portal survey will be anonymous and no study ID or PHI will be entered. In addition to the survey, chart review data will be collected which contains information about each provider's practice patterns. These data are collected once every 3 months, in both arms. These data include number of children screened for ASD and number of children referred to EI/ECSE for an ASD concern. Note that referrals to Early Intervention are a separate process that is standard of care, and is not related to enrollment in the study. Providers will be encouraged to adhere to standard of care in terms of screening children for autism and referring to Early Intervention; however this process can be accomplished by usual methods without enrolling children in the study if providers prefer. Number of children screened for ASD, and screening test results, will be collected by a practice administrator, using an existing form that we have used in prior research projects. The administrator will be considered engaged in research through an IAA. This form will be encrypted and sent to the study team electronically using OHSU's secure server. Finally, fidelity data (e.g., PCP-Navigator Contact Log) will contain information about interactions between the PCP and the navigator. This file will be kept encrypted and stored on OHSU Box, a secure cloud server.

Follow-up provider interviews: Using data already collected from participating clinics, study team members will review referral rate data from all 41 participating pediatricians and stratify each according to referral rates; then, we will identify the highest-referring (top) and lowest referring (bottom) quartiles. High- and low-referring pediatricians will be invited to participate in a video qualitative interview, via email solicitation from the study team. **Providers will be emailed the information sheet as part of their study invitation; the information sheet will be reviewed and a verbal consent will be recorded prior to the interview.** They will be compensated **\$100 via clincard** for participation after the interview. The interview will use Chart Stimulated Recall, a case-based interviewing technique which explores clinical reasoning and management decisions by guiding pediatricians to reflectively review medical records. For each pediatrician, the study team will select 2-3 patients with positive screens to Early Intervention services. With the study team, the pediatrician will review each patient's chart to discuss their recollection of the screening process, and why they did/did not refer the child to EI. The interviewer will also ask general questions regarding decision making about positive screens. All interviews will be recorded and professionally transcribed for analysis.

The pediatrician interview will last 45 minutes and use CSR methods. CSR, derived from the field of medical anthropology, is a case-based interviewing technique which explores clinical reasoning and management decisions by guiding pediatricians to reflectively review patient medical records. It permits patient, environmental, system, and other factors that can influence clinical decisions to emerge. CSR has been successfully used in other primary care research settings, such as with HIV screening. For each pediatrician, the study team will use the Autism ALERT database to select 2-3 of their patients who screened positive for ASD. Guided by the study team, the pediatrician will review each patient's chart notes **with PHI redacted** to discuss their recollection of the screening process, and why they either ultimately choose to refer or not

refer the child to Early Intervention Services. At the end of the CSR, the interviewer will ask general questions regarding decision making about positive ASD screens.

Qualitative Interview process. Interviews will be via telephone or videoconference **on Webex**, per subject preference, and last approximately 45 minutes. Immediately after each interview, the interviewer will create a structured memo describing the interview's key findings, interviewer reflections, and areas for future investigation. Memos will be distributed to all team members for review. All interviews will be recorded and professionally transcribed for analysis.

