### **e) Recruitment Methods**

The study has a clinic-based recruitment strategy. In order to assure that the intervention addresses the needs of diverse children who are underserved in autism care, study inclusion criteria mandate that participating clinics have at least 50% Medicaid or uninsured patients. In addition, to make sure sample size is adequate, Family Medicine clinics must have at least 30% children. Since one of the study's goals is to ultimately reduce racial and ethnic disparities in the early identification of ASD, we will strive to attain a racially and ethnically diverse family sample by specifically approaching clinics that serve a diverse patient base, including recruiting clinics in rural areas. Autism ALERT will initially be offered to all Oregon primary care clinics meeting inclusion criteria in selected counties. We seek to enroll 6 clinics; if more than 6 clinics initially express interest, we will randomly choose 6 interested clinics, reserving at least two spots for non-urban clinics. If fewer than 6 express interest, we will open recruitment to additional counties. In this way, we hope to recruit a sample that would be representative of primary care clinics who will ultimately participate in a larger-scale study.

Clinics will be recruited to the study with the help of the Oregon Pediatric Society. They will be approached initially via an approved recruitment email (see "Autism ALERT Email Templates"). The recruitment process will include a training session for all clinic staff, at which initial provider surveys and patient study packets will be distributed.

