Families will initially receive a study packet from their provider at the time of the referral. The packet will contain a children's book, information about autism, an Early Intervention Referral Form, and a Study Interest Form. Aside from the study interest form and the phone scripts that are used for screening there are no other recruitment materials (e.g., emails, flyers) for family participants at this time. They will learn about the study first from the study interest form. The Study Interest Form will include some general information about the study, as well as a HIPAA authorization allowing disclosure of family contact information and some health information to the study team. The parent will sign the interest form, allowing the clinic to pass the family's contact information to the Navigator team. Navigators will then reach out to the family to complete the online consent process, or phone consent process as necessary (see more information below). Please see Family Consent Form attachments. Family enrollment will be incentivized with a children's book and \$50 stipend per survey completed for both experimental and control groups. Provider participants may receive Continuing Medical Education credits and/or Part IV Maintenance of Certification credits, if desired, as part of their participation in this study. Clinics may also be entered into a raffle to incentivize their patients' referral to the study, based on whether they refer any patients to the study in a given time period. The raffle incentive will be a gift or food basket costing less than \$100. Control arm clinics will also be given a box of chocolate on Valentine's day to further increase enrollment as enrollment is lagging in that arm.

For clinics in the OHSU system, referrals to the Autism diagnostic clinic will also be monitored for potential study recruitment. The diagnostic clinic staff will provide a list of MRNs of patients referred to the OHSU Autism Clinic, which will be transmitted via secure OHSU emails to the referring primary care provider and study team for inclusion in the study. Data will be transmitted as a list of MRNs, which the provider can use EPIC to identify and consider. If the provider gives permission, the study team will directly contact the family. No PHI will leave OHSU.

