##### Families:

The consent process for families (in the intervention and control groups) was different than that for primary care providers. Families for whom ASD is suspected will be handed a study interest form by their PCP. The PCP will ask if they are interested in learning more about the study. If so, they will indicate their interest by completing a study interest form. This study interest form will serve as authorization to allow the PCP to release information to the researchers for recruitment purposes. This signed interest form signifies study interest but is not a consent for the study. Interested parents will then be contacted by the study team via phone, text or email, to secure electronic signed consent or verbal consent.

Text messaging, using the secure Twilio app hosted by OHSU, will be utilized for scheduling phone calls. Text messaging will not be used to obtain consent but will be used to schedule a phone appointment to obtain consent. After consenting, the family may also choose to receive text messages from the navigator or study team with updates, reminders, or other scheduling requests.

**Electronic consent:** Families will sign consent electronically through a form built in Research Electronic Data Capture (REDCap). The software allows consent forms to be emailed directly to the email address that the participant provides upon signing the Study Interest Form. Per OHSU OCTRI requirements, participants will click a radio-box for yes or no, and if yes is selected, will enter their first and last name. This will be used in conjunction with the timestamp on the REDCap form to confirm consent to the study. In most cases, participants will provide electronic consent while on the phone with a Navigator, who will be able to confirm their identity through phone, email, and signature congruency.

**Verbal Consent over the Phone:** For families lacking internet access, a verbal consent via telephone will be provided in lieu of electronic signed consent. For these families we have requested a HIPAA waiver/alteration.

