## **8) Data Analysis**

Process data from CCMT and Navigator Fidelity Checklist will be used to calculate contact attempts, time to first contact, total time spent per family, and counts of specific navigator activities. Families who complete all calls will be compared to those who broke off contact, and specific points of participant drop-off will be calculated. We will assess whether specific intervention activities varied by family demographic characteristic and clinic site, to assess variability in acceptability, using bivariate analyses. Family survey data will also be used to assess feasibility and acceptability. Initial analyses will focus on families who participated in ALERT, assessing experience of care and improvement suggestions. Next, post-intervention family experience will be compared in intervention vs. control clinics using bivariate analyses with an intention-to-treat approach. We will also examine variation in experience outcomes overall, and by study arm, by demographic characteristics, in order to assess whether the intervention was appropriate for diverse families, and to target improvements. Parent responses to open-ended items will be assessed via conventional content analysis. Using the parent interviews, we will also qualitatively assess families' feelings towards the evaluation process, and for the intervention arm we will also be looking at experiences with family navigators.

PCP process data will be used in a similar fashion. PCP/Navigator interactions will be descriptively characterized, using the PCP-Navigator Con-tact log and use of the PCP Website. PCP survey data will be used to characterize PCPs' post-intervention experiences. PCPs' overall experiences will be compared in both arms using bivariate testing, and open-ended questions will be coded.

We will refine our mechanism hypotheses and measurement by examining change in family-and provider-reported outcomes (e.g., stress, empowerment) pre-and post-intervention, in both study arms, primarily using descriptive and bivariate tests. Exploratory analyses will assess whether mechanism outcomes differ by family race/ethnicity, English proficiency, or insurance type, both overall and by study arm, using bivariate or limited multivariable regression analyses. This will allow us to gather valuable descriptive data on variation in engagement of target mechanisms, which might allow for individualized messaging in future research.

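### The survey procedures do not ensure that the pre-intervention family and provider surveys are completed before exposure, so pre/post change in the mechanism outcomes may be distorted

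*Protocol*

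**What the plan says.** **Families.** Protocol section 6 (Procedures) collects the survey by mail or online and fixes its timing by dispatch: "The survey will be sent upon enrollment and 6 months after enrollment in Autism ALERT or the comparison intervention". The expansion keeps the same two time points. No completion window is given, and no order is set between the first survey and the start of navigation. Follow-up is described as "The survey will initially be sent 3 times via a secure RedCap link. Then non-responders will be contacted via telephone", and then "Subjects who do not respond to either email or telephone will be sent a survey mailing".

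On enrolment, section 5(e) says "Navigators will then reach out to the family to complete the online consent process, or phone consent process as necessary", and section 5(f), Families, adds "In most cases, participants will provide electronic consent while on the phone with a Navigator".

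**Providers.** Section 5(e) describes "a training session for all clinic staff, at which initial provider surveys and patient study packets will be distributed". Section 6 places the first provider survey at enrolment. It also provides for reminder emails to non-responders and for return by mail or fax, without limiting this to the final survey. Section 5(f), Providers, lets those who missed the meeting join later by electronic form.

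**Use of the scores.** Section 8 (Data Analysis) plans to refine the mechanism hypotheses by "examining change in family-and provider-reported outcomes (e.g., stress, empowerment) pre-and post-intervention, in both study arms".

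**The concern.** A pre-score is a baseline only if it is taken before the intervention can act. Here the timing is tied to when the survey is sent, and for providers to the event that delivers the training. A parent who answers some time after consent may already be working with a navigator. A provider who answers during or after the session may already have been taught.

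If so, part of the effect sits in the baseline and is subtracted out of the change score. A weak mechanism signal could then not be told apart from a contaminated baseline. In the pilot, navigation goes to one arm only, so the between-arm comparison of family change is exposed too. In the expansion there is no control group against which to see the problem. An analysis plan can flag or set aside late surveys afterwards, but it cannot recover a baseline that was not collected in time.

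**Working it through.** The protocol states no effect size, power or change score for these outcomes, so there is no figure of its own to reproduce. The check has two parts: what the text allows, and how large the consequence could be.

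**1. Can a first survey follow exposure?**
- *ALERT families:* yes. Consent comes first and the survey is sent at enrolment. Navigation may start at any time after consent, and no rule links the survey to that start.
- *Control families:* not through navigation, because section 4 gives that arm START Autism only. The referral packet in section 5(e) comes before enrolment and is not limited to one arm, so it does not separate the arms.
- *Providers, both arms:* yes. The survey is distributed at the training with no stated order relative to the teaching, and later return is allowed. Section 10(b) confirms that both arms are trained.

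**2. What would it do to the change score?**
Let D be the true intervention-related change at follow-up, f the share of first surveys completed after exposure, and g the share of D already present at that survey. The mean pre-score moves by f × g × D, so

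observed change = D − f × g × D = D × (1 − f × g).

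For pilot families the control pre-scores are not moved by navigation, so the between-arm contrast shrinks by the same factor.

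The values of f, g and D = 0.50 (in SD units) are assumptions; none is in the protocol. To show what a planner would see if such a d were carried forward, the last column gives n per arm = 2 × (1.960 + 0.842)² / d² = 15.70 / d², rounded up (two-sided 5%, 80% power).

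| f | g | f × g | observed d | n per arm |
|---|---|---|---|---|
| any | 0 | 0 | 0.500 | 63 |
| 0.1 | 0.1 | 0.01 | 0.495 | 65 |
| 0.3 | 0.3 | 0.09 | 0.455 | 76 |
| 0.5 | 0.5 | 0.25 | 0.375 | 112 |
| 0.3 | −0.2 | −0.06 | 0.530 | 56 |
| 0.5 | −0.2 | −0.10 | 0.550 | 52 |

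The last two rows show an early effect of opposite sign, for example a temporary rise in stress. Change is then overstated.

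**3. Providers.** Suppose START changes a score by 0.40 in both arms and ALERT adds 0.20, with f = 0.5 and g = 0.3. The START change is observed as 0.40 × (1 − 0.15) = 0.34 in each arm. The between-arm contrast stays at 0.20 if only START content comes before the survey. It falls to 0.20 × 0.85 = 0.17 if ALERT content does too.

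**4. Scale against sampling error.** Section 5(a) plans 25 dyads per arm. At d = 0.50 the standard error of d is about √(50/625 + 0.25/100) = √0.0825 = 0.29. The shift from 0.50 to 0.455 is 0.045, about 0.16 of one standard error. The shift to 0.375 is 0.125, about 0.44.

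**The case against.** The best case on the other side is that the protocol is silent on order, not wrong about it, and that silence supports less than it may seem to. Several stronger readings are tempting, and the text does not support them.

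- *That change is biased toward zero.* The protocol gives no share of late surveys, no early effect and no sign. Section 10(b) expects navigators to raise empowerment and self-efficacy, which makes attenuation plausible there, but stress could move the other way at first.
- *That the consent call is itself exposure.* Section 5(f) gives the navigator a consent and identity role on that call and describes the process for both arms. For children referred by their primary care provider in the expansion, consent is sought by a team member. Only navigation after consent is specific to ALERT.
- *That the first survey is certainly chased by link, telephone and mail.* Those sentences follow the text on the six-month letter and may mainly describe that survey. The gap does not depend on them, since a survey sent by link or mail with no deadline can come back late anyway.
- *That the distortion is mainly in the ALERT arm.* This fits families only.
- *That providers answer after being taught.* They may answer before. Those who missed the meeting had not had that teaching when they joined, so they are not evidence of contamination.
- *That pre/post is the only contrast in the expansion.* Section 8 also compares families who engaged with those who did not.

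It is also fair that little rests on these scores. The primary outcomes are feasibility and acceptability, the mechanism analyses are mainly descriptive, and the pilot is deliberately not powered. Completion windows can be left to an analysis plan. What stands is narrower: the collection procedure is fixed in the protocol, it permits a baseline taken after exposure, and section 8 names the result pre-intervention.

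**Conclusion.** The point holds in a limited form. The protocol does not ensure that first surveys precede exposure, for ALERT families (pilot arm and expansion) or for providers in both arms. Pre/post change in the mechanism outcomes may therefore be distorted, and is probably attenuated if early effects share the sign of the six-month effect. With no late surveys or no early effect there is no bias.

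The size cannot be stated. The illustrative range runs from a 1% loss (f = g = 0.1) to a 25% loss (f = g = 0.5), and to a 10% exaggeration if the early effect is reversed. At 25 dyads per arm these shifts are smaller than the sampling error, but extra families do not remove a systematic shift, and the expansion expects around 300 children.

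The primary feasibility and acceptability outcomes, the post-only family experience comparison and the ecWeb outcomes do not use the first survey and are not affected. The case for acting is that prevention is cheap and later repair is only partial.

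**What to change.** - *Families, both arms:* offer the enrolment survey in the same REDCap session or call as consent, before any navigation content. Do not hold navigation back for families who postpone it.
- *Providers, both arms:* collect the initial survey before the teaching starts, and before a late joiner's own training.
- *Dates:* record the completion date of each first survey. Set it against the first post-consent navigation contact, taken from the Care Coordination Management Tool, or against the training date for providers.
- *Analysis:* keep all families in the main change analysis and repeat it without late first surveys as a sensitivity analysis. Define late by the same number of days since enrolment in both arms. A rule based on first navigation contact that set pre-scores to missing could act only in the ALERT arm, since controls have no such date, and would remove late responders from one side of the comparison.

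The cost is a slightly longer consent call and one extra sensitivity analysis. No new instrument is needed: REDCap already timestamps consent, and the navigator process data already yield time to first contact.
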